### **Lost to Follow-Up**

For subjects to be considered lost to follow-up, reasonable attempts must be made to obtain information on the final status of the subject. At a minimum, two phone calls must be made and one certified letter must be sent and documented in the subject's source documentation.

## **5.4.2 Discontinuation of Entire Study**

AbbVie may terminate this study prematurely, either in its entirety or at any study site, for reasonable cause provided that written notice is submitted in advance of the intended termination. The Investigator may also terminate the study at his/her site for reasonable cause, after providing written notice to AbbVie in advance of the intended termination. Advance notice is not required by either party if the study is stopped due to safety concerns. If AbbVie terminates the study for safety reasons, AbbVie will immediately notify the Investigator by telephone and subsequently provide written instructions for study termination.

## **5.5 Treatments**

### **5.5.1 Treatments Administered**

There are two active study drugs in this study. The first is daily upadacitinib (ABT-494) and the second is ADA eow.

Upadacitinib (ABT-494) (or matching placebo) study drug will be taken orally once daily, beginning on Day 1 (Baseline), and should be taken at approximately the same time each day. The study drug can be taken with or without food. Subjects will continue their weekly stable background therapy of MTX. AbbVie will not supply MTX nor folic acid (or equivalent, such as folinic acid).

ADA (or matching placebo) will be provided as a subcutaneous injection solution in 1 mL pre-filled syringes containing ADA 40 mg/0.8 mL (or matching placebo). ADA (or matching placebo) will be subcutaneously administered eow at approximately the same time of day.

Subjects should take a dietary supplement of oral folic acid beginning on Day 1 (Baseline) throughout study participation. Folic acid dosing and timing of regimen should be followed according to the Investigator's instructions.

Subjects will receive both oral study drug QD (either upadacitinib (ABT-494) 15 mg or matching placebo) and subcutaneous study drug eow (either ADA 40 mg or matching placebo). When the last subject completes the last visit of Period 1 (Week 48), study drug assignment in both periods will be unblinded to the Sponsor and sites, and subjects will be dispensed study drug in an open-label fashion until the completion of Period 2.

### **5.5.2 Identity of Investigational Product**

The individual study drug information is presented in [Table 6](#).

**Table 6. Identity of Investigational Product**

Investigational Product	Mode of Administration	Formulation	Strength	Manufacturer
Upadacitinib (ABT-494)	oral	tablet	15 mg	AbbVie
Upadacitinib (ABT-494) matching placebo	oral	tablet	NA	AbbVie
Adalimumab	subcutaneous injection	Adalimumab/Mannitol, Citric acid monohydrate, Sodium citrate, Disodium phosphate dihydrate, Sodium dihydrogen phosphate dihydrate, Sodium chloride, Polysorbate 80, Water for injections, Sodium hydroxide added as necessary to adjust pH	40 mg/0.8 mL	AbbVie or Vetter
Adalimumab matching placebo	subcutaneous injection	Mannitol, Citric acid monohydrate, Sodium citrate, Disodium phosphate dihydrate, Sodium dihydrogen phosphate dihydrate, Sodium chloride, Polysorbate 80, Water for injections, Sodium hydroxide added as necessary to adjust pH	NA	AbbVie or Vetter

### 5.5.2.1 Packaging and Labeling

Upadacitinib (ABT-494) and matching placebo will be packaged in bottles with quantities sufficient to accommodate study design. Each kit label will contain a unique kit number. This kit number is assigned to a subject via IRT and encodes the appropriate study drug to be dispensed at the subject's corresponding study visit. Each kit will be labeled as required per country requirements. Labels must remain affixed to the kits. All blank spaces on the label will be completed by the site staff prior to dispensing to the subjects.

ADA will contain 2 pre-filled syringes of ADA 40 mg/0.8 mL or matching placebo per carton. Each kit label will contain a unique kit number. This kit number is assigned to a subject via IRT and encodes the appropriate study drug to be dispensed at the subject's corresponding study visit. Each kit will be labeled as required per country requirements. Labels must remain affixed to the kits. All blank spaces on the label will be completed by the site staff prior to dispensing to the subjects.

#### **5.5.2.2 Storage and Disposition of Study Drugs**

Upadacitinib (ABT-494) must be stored at controlled room temperature (15° to 25°C/59° to 77°F). ADA must be stored protected from light at 2° – 8°C (36° – 46°F). Study drug must not be frozen at any time. The investigational products are for investigational use only and are to be used only within the context of this study. The study drug supplied for this study must be maintained under adequate security and stored under the conditions specified on the label until dispensed for subject use or destroyed on site as appropriate.

#### **5.5.3 Method of Assigning Subjects to Treatment Groups**

All subjects will be randomized using IRT. Before the study is initiated, IRT directions will be provided to each site.

All subjects will be assigned a unique identification number by the IRT at the Screening Visit. For subjects that re-screen, the Screening number assigned by the IRT at the initial Screening visit should be used; a new Screening number should not be requested.

Subjects will be eligible for randomization if they continue to meet all of the selection criteria (Section 5.2) at Baseline and are willing to continue in the study.

Subjects will be randomized in a 2:2:1 ratio using interactive response technology (IRT) to receive double-blind study drug in one of the following treatment groups:

- Group 1: Upadacitinib (ABT-494) 15 mg QD (N = 600)
- Group 2: Placebo (N = 600)
- Group 3: ADA (40 mg eow) (N = 300)

Subjects will receive both oral study drug QD (either upadacitinib 15 mg or matching placebo) and subcutaneous study drug eow (either ADA 40 mg or matching placebo) until the study is unblinded.

Randomization will be stratified by prior bDMARD exposure (yes or no) and geographic region.

The IRT will assign a randomization number that will encode the subject's treatment group assignment according to the randomization schedule generated by the Statistics Department at AbbVie.

IRT will provide the appropriate study drug kit number(s) to dispense to each subject. Study drug will be administered at the study visits as summarized in Section 5.3.1.1. Returned study drug should not be re-dispensed to any subject.

#### **5.5.4 Selection and Timing of Dose for Each Subject**

Subjects should take study drug as outlined in Section 5.5.1.

On dosing days that occur on study visit days, subjects should follow the regular dosing schedule (refer to Section 5.3.2.1 regarding Week 2 and Week 4 visits).

Each subject's dosing schedule should be closely monitored by the site at each study visit by careful review of the subject's dosing diary. This will ensure that all subjects enrolled into the study maintain their original dosing schedule beginning with the first dose of study drug (Baseline/Day 1).

Upadacitinib/Placebo (daily dosing):

- If a subject should forget to take their upadacitinib (ABT-494) (or matching placebo) dose at their regularly scheduled dosing time, they should take the forgotten dose as soon as they remember the dose was missed as long as it is at least 10 hours before their next scheduled dose. If a subject only remembers

the missed dose within 10 hours before next scheduled dose, the subject should skip the missed dose and take the next dose at the scheduled time.

- If the subject experiences a study drug interruption > 14 consecutive days during the first 26 weeks, > 21 days between Week 26 and Week 48 or > 30 consecutive days during Period 2 (other than for reasons listed in Section 6.1.7), they should notify their study site physician, and the subject should be discontinued from study drugs. If study treatment drug is interrupted or withdrawn in Periods 1 or 2, both oral and subcutaneous study drug administration must be stopped.

ADA/Placebo (biweekly dosing):

- Biweekly ADA (or matching placebo) should be injected the same day and approximately the same time every other week. If the subject should forget to inject their subcutaneous study drug on their regularly scheduled dosing date, they should inject the forgotten dose as soon as they remember the dose was missed up to the day before their scheduled dose. The subject must not administer two injections on the same day.
- If the subject experiences a study drug interruption of > 2 consecutive missed doses during the first 26 weeks or > 3 consecutive missed doses after Week 26 (other than for reasons listed in Section 6.1.7), they should notify their study site physician, and the subject should be discontinued from the study. If study treatment drug is interrupted or withdrawn in Periods 1 or 2, both oral and subcutaneous injections must be stopped.

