### **5.0 Investigational Plan**

#### **5.1 Overall Study Design and Plan: Description**

This is a Phase 3 multicenter study that includes two periods. Period 1 is a 48-week randomized, double-blind, parallel-group, placebo-controlled and active comparator-controlled period designed to compare the safety and efficacy of upadacitinib 15 mg QD versus placebo and versus ADA for the treatment of signs and symptoms of subjects with moderately to severely active RA who are on a stable dose of MTX and have an inadequate response to MTX (MTX-IR). Period 1 is also designed to compare the efficacy of upadacitinib 15 mg QD versus placebo for the prevention of structural progression. Period 2 is a long-term extension to evaluate the safety, tolerability and efficacy of upadacitinib 15 mg QD in subjects with RA who have completed Period 1.

The study is designed to enroll approximately 1500 subjects at approximately 510 study centers worldwide to meet scientific and regulatory objectives without enrolling an undue number of subjects in alignment with ethical considerations. Therefore, if the target number of subjects has been enrolled, there is a possibility that additional subjects in screening will not be enrolled.

The study duration will include a 35-day screening period; a 48-week randomized, double-blind, parallel-group, placebo-controlled and active comparator-controlled treatment period (Period 1); a long-term extension period (blinded until the last subject completes Period 1) (up to 5 years) (Period 2); a 30-day follow-up period (call or visit); and a 70-day follow-up call.

Subjects who meet eligibility criteria will be randomized in a 2:2:1 ratio to one of three treatment groups:

- Group 1: Upadacitinib (ABT-494) 15 mg QD (N = 600)
- Group 2: Placebo (N = 600)
- Group 3: ADA (40 mg every other week [eow]) (N = 300)

Subjects will receive both oral study drug QD (either upadacitinib 15 mg or matching placebo) and subcutaneous study drug eow (either ADA 40 mg or matching placebo) until the study is unblinded.

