An unblinded analysis will be conducted after all subjects have completed Week 26 for the purpose of regulatory submission. To maintain integrity of the trial and avoid introduction of bias, study sites and subjects will remain blinded for the duration of Period 1. Additional unblinded analyses may be conducted after the Week 26 unblinded analysis for regulatory purposes.

Each subject will undergo a maximum of 5 scheduled visits for x-ray examination of bilateral hands and feet during Period 1 (unless unscheduled repeat imaging is needed due to failure to meet the quality requirements) at Screening, Week 26, and Week 48/Premature Discontinuation. Subjects who are non-responders (defined as those not achieving  $\geq 20\%$  improvement in TJC and SJC criterion) at Week 14 and are switched to rescue therapy will have an x-ray examination at Week 14; in addition, subjects who prematurely discontinue from study drug or the study [REDACTED] will have an x-ray examination at the premature discontinuation timepoint (refer to Section 5.3.1.1 for additional details).

Joint x-rays will be sent to the central imaging vendor designated by the Sponsor. The x-rays will only be assessed by the imaging vendor for erosions and joint space narrowing, and will not be assessed for any other clinically significant findings that may impact a subject's health.

[figure not shown]
Subjects who complete the Week 48 visit (end of Period 1) will enter the long-term extension portion of the study, Period 2 (up to 5 years). Subjects will continue study treatment as assigned in Period 1. Subjects who are assigned to the upadacitinib 15 mg

QD treatment group at the end of Period 1 will continue to receive upadacitinib 15 mg QD in a blinded manner. Subjects who are assigned to adalimumab 40 mg eow at the end of Period 1 will continue to receive adalimumab 40 mg eow in a blinded manner. When the last subject completes the last visit of Period 1 (Week 48), study drug assignment in both periods will be unblinded to the Sponsor and sites, and subjects will be dispensed study drug in an open-label fashion until the completion of Period 2.

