### **Discontinuation of Study Drug and Continuation of Study Participation (Period 1 and Period 2)**

Subjects may discontinue study drug treatment, but may choose to continue to participate in the study (refer to Section 5.4.1 for additional details). Subjects who prematurely discontinue study drug should complete a Premature Discontinuation Visit (PD visit) as soon as possible, preferably within 2 weeks. Afterwards, subjects should follow the regular visit schedule as outlined in Table 2 and Table 4, and adhere to all study procedures except for dispensing study drug, PK sample collection, and blood sample collection for optional exploratory research and validation studies. In addition, all future rescue and efficacy-driven discontinuation criteria no longer apply; this includes 20% TJC/SJC calculations at Weeks 14 – 22, and Week 48 and thereafter, as well as CDAI calculation at Week 26, if applicable. If at any point a subject no longer wants to provide assessments (withdrawal of informed consent) following discontinuation of study drug, a second PD visit is not required.

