- Starting at Week 48, at least 20% improvement in BOTH TJC AND SJC compared to baseline is required to remain on study drug. Anyone who does not fulfill this criterion at 2 consecutive visits (starting at Week 48) must be discontinued from study drug.

In order to minimize missing data for efficacy and safety assessments, subjects who prematurely discontinue study drug treatment or study participation should complete a Premature Discontinuation visit (PD visit) as described in Section 5.1 (Overall Study Design and Plan: Description)

All attempts must be made to determine the date of the last study drug dose and the primary reason for discontinuation of study drug or study participation. The information will be recorded on the appropriate eCRF page. However, these procedures should not interfere with the initiation of any new treatments or therapeutic modalities that the Investigator feels are necessary to treat the subject's condition. Following discontinuation of study drug, the subject will be treated in accordance with the Investigator's best clinical judgment, irrespective of whether the subject decides to continue participation in the study.

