### **6.1.7 Toxicity Management**

The toxicity management of the AEs including AEs of special interest consists of safety monitoring (review of AEs on an ongoing basis, and periodical/ad hoc review of safety issues by a safety data monitoring committee), interruption of study drug dosing with appropriate clinical management if applicable, and discontinuation of the subjects from study drug. The management of specific AEs and laboratory parameters is described below.

For subjects who discontinued study drug but continued study participation and are instead on standard of care therapies, these toxicity management requirements do not apply (including alerts from the central lab) and any intolerability to standard of care therapies should be managed by the prescribing physician.

**Serious Infections:** Subjects should be closely monitored for the development of signs and symptoms of infection during and after treatment with study drug. Study drug should be interrupted if a subject develops a serious infection or an opportunistic infection. A subject who develops a new infection during treatment with study drug should undergo prompt diagnostic testing appropriate for an immunocompromised subject. As appropriate, antimicrobial therapy should be initiated, and the subject should be closely monitored. Re-challenge with study drug may occur once the infection has been successfully treated. If study drug has been interrupted for a serious infection for more than 14 consecutive days during the first 26 weeks, more than 21 days between Weeks 26 and 48 or more than 30 consecutive days thereafter, the subject must be discontinued from study drug. Subjects who develop active TB must be permanently discontinued from study drug.

**Gastrointestinal Perforation:** Subjects presenting with the onset of signs or symptoms of a serious gastrointestinal event should be evaluated promptly for early identification of

gastrointestinal perforation. If the diagnosis of gastrointestinal perforation is confirmed, the subject must be discontinued from study drug.

**Cardiovascular Events:** Subjects presenting with potential cardiovascular events should be carefully monitored. These events will be reviewed and adjudicated by an independent Cardiovascular Adjudication Committee in a blinded manner.

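### The missed-injection rule in Protocol 5.5.4 removes subjects from the study, where the parallel tablet rule stops study drug only; read literally, it ends scheduled off-drug follow-up for what is likely a very small number of subjects

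*Protocol*

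**What the plan says.** Protocol 5.5.4 has two bullets on over-long interruptions, one for tablets and one for injections. Both exempt the reasons listed in Section 6.1.7. The tablet bullet ends "the subject should be discontinued from study drugs"; the injection bullet ends "they should notify their study site physician, and the subject should be discontinued from the study". The next sentence of the injection bullet speaks only of drug: "If study treatment drug is interrupted or withdrawn in Periods 1 or 2, both oral and subcutaneous injections must be stopped".

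Elsewhere the protocol separates stopping drug from leaving the study. Section 5.1 says: "Subjects may discontinue study drug treatment, but may choose to continue to participate in the study". Those who stay follow the regular visits without study drug, pharmacokinetic samples or optional research samples. Section 5.4.1 gives the purpose of the premature discontinuation (PD) visit: "In order to minimize missing data for efficacy and safety assessments". For an over-long interruption due to serious infection, Section 6.1.7 stops drug only: "more than 30 consecutive days thereafter, the subject must be discontinued from study drug".

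This is current text. Amendment 5 changed the dose counts in the injection sentence (Protocol Appendix P) and kept its ending.

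**The concern.** Missing injections is a dosing event. It is not a withdrawal of consent, and nothing in the protocol explains why it should end participation when missing tablets does not. A site that applies the sentence as written would take the subject off the visit schedule and deny the choice given in Section 5.1.

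At stake is information collected after drug is stopped: clinical assessments, hand and foot x-rays, and the adverse events that Protocol 6.1.4 collects for as long as an off-drug subject stays in the study. Because of the double dummy, all three arms are exposed to the rule during the blinded part of the trial.

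**Working it through.** **1. The rules side by side**

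| Place | Trigger | Outcome |
|---|---|---|
| Protocol 5.5.4, tablets | >14 consecutive days (first 26 weeks), >21 days (Weeks 26 to 48), >30 consecutive days (Period 2) | off study drugs |
| Protocol 5.5.4, injections | >2 consecutive missed doses (first 26 weeks), >3 after Week 26 | off the study |
| Protocol 6.1.7, serious infection | >14, >21, >30 days in the same three spans | off study drug |
| Protocol 6.1.7, adverse events and surgery | up to 2, later up to 3, missed injections allowed | none stated |

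Only the injection bullet ends participation.

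**2. Who is reached**

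- Subjects who miss injections but keep taking tablets. The tablet limit never applies to them, so the injection clause decides the outcome.
- Adalimumab subjects in open-label Period 2. Section 5.1 gives tablets "and subcutaneous study drug eow (either ADA 40 mg or matching placebo) until the study is unblinded"; afterwards "subjects will be dispensed study drug in an open-label fashion until the completion of Period 2". This implies, though it does not state, that these subjects then have no tablets and so no tablet limit.

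**3. What a subject who leaves the study still provides**

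Under Protocol 5.1 a PD visit should take place. A 30-day visit or call may follow, as may a 70-day call for subcutaneous drug. Under Protocol 6.1.4, adverse events are collected to 30 days after the last oral dose and 70 days after the last subcutaneous dose. The loss is what would have come after that.

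**4. Which analyses would change**

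| Analysis | Off drug, still followed | Out of the study | Difference |
|---|---|---|---|
| Non-responder imputation (NRI), primary (SAP 9.1.2, 9.2.1) | non-responder at all later visits | same | none |
| Observed Cases (SAP 9.1.2) | values after drug stop excluded | same | none |
| Week 26 mTSS, linear extrapolation (SAP 9.3.2) | extrapolated from earlier films | same | essentially none; the PD timing condition is redacted |
| As Observed efficacy and x-rays, Period 1 (SAP 9.1.2, 9.3.2, 9.3.3) | used | missing | lost |
| Long-term efficacy, As Observed (SAP 9.4) | used | missing | lost; descriptive, no testing |
| Short-term adverse event sensitivity summaries (SAP 10.2.1.1, 10.2.1.2) | all events after first dose | events within the 30/70 days | later events lost, for cases before Week 26 only |
| Long-term adverse event rates (SAP 10.2, 10.2.2) | events within 30/70 days | same | none by definition |
| Mixed-model and multiple-imputation endpoints (SAP 9.1.2) | details redacted | details redacted | cannot be read |

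**5. Size**

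The plan gives no rate for long runs of missed injections, so there is no figure of its own to reproduce on this point. For scale only, assume 0.25% to 3% of 1500 subjects: 1500 × 0.0025 = 3.75 (about 4) to 1500 × 0.03 = 45.

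Take the Week 26 mTSS comparison: difference 0.39, SD 2, 600 per arm less 10% dropout, so n = 540. Power is Φ(0.39 / (2√(2/n)) − 1.96).

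- n = 540: 0.39 / 0.1217 = 3.204; Φ(1.244) = 89.3%, which matches the stated approximately 90%.
- A further 3% lost entirely, n = 600 × 0.87 = 522: 0.39 / 0.1238 = 3.150; Φ(1.190) = 88.3%.

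This overstates the effect, because these subjects can still have a PD film and the controlled analysis extrapolates from earlier films.

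**The case against.** **The wording is probably a slip.** Section 5.1 ties leaving the study to withdrawal of informed consent, and the sentence after the clause is about drug only. The protocol is loose about leaving the study elsewhere: in the laboratory-test text of 5.3.1.1, in the adverse event definition of 6.1.1.1, and in 5.4.1, where withdrawal from the trial sits in a list of reasons to stop drug. All of this stands. A site may already read the clause as drug only, so the literal consequence is not certain. The mismatch remains, in a sentence that sites are told to apply.

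**Section 6.1.7 is not a competing rule.** This also stands. Its serious-infection sentence covers subjects whom the injection clause exempts, so it shows the protocol's general practice and no more. The direct comparison is with the tablet bullet.

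**A reader might infer that the clause can hardly ever act.** If tablets stop on the day of the first missed injection (Day 1), the tablet limit is passed first. In the first 26 weeks that is Day 15, against a third miss on Day 29. In Weeks 26 to 48 it is Day 22, against a fourth miss on Day 43. In Period 2, while both drugs are given, it is Day 31 against Day 43. This does not bound the reach. It treats every forgotten injection as an interruption that requires tablets to stop, whereas 5.5.4 handles forgetting separately (inject when remembered, up to the day before the next dose) and does not tell the subject to stop tablets. It also says nothing about open-label adalimumab.

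**A reader might infer the opposite, that the clause ends all follow-up or threatens the main results.** The documents do not support that either: the PD visit and safety contacts remain, and the primary analysis treats the subject identically on both routes. Nor can Period 2 cases enter the short-term adverse event sensitivity summaries, which stop at Week 26.

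**Conclusion.** The inconsistency is real and minor. Read literally, the injection clause removes scheduled off-drug follow-up beyond the PD visit and the 30/70-day contacts, for an unknown but likely very small number of subjects. *Likely very small* is a judgement; the documents supply no count. The Period 2 route rests on the inference that open-label adalimumab subjects take no tablets.

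It would be too strong to say that the loss is confined to As Observed data. It falls mainly there and on later off-drug adverse events, but with the mixed-model and multiple-imputation details redacted, an effect on those continuous endpoints can be neither shown nor excluded. No effect on the primary result or on multiplicity control is shown.

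**What to change.** In the injection bullet of Protocol 5.5.4, replace *from the study* with *from study drugs*, so that it ends as the tablet bullet does. Make the change in the next amendment, with a short notice to sites. The safety action, stopping both drugs, does not change, and neither does the SAP.

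Optional and editorial only: Table 2 note r sends pregnant subjects out of the study at any visit. Section 5.3.1.1, to which the note points, does so only for a confirmed positive test at Baseline and stops drug after Baseline; Table 4 note j, 5.4.1 and 6.1.6 also stop drug only. One footnote sentence would align note r, but a site that follows the pointer already gets the right answer.
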